#### B. Feasibility:

The following feasibility data will be collected and assessed :

- 1) Recruitment:
  - a. Recruitment sites (number, location, and method of their selection)
  - b. Factors influencing recruitment rate
  - c. Methods used for subject recruitment
  - d. Number of subjects:
    - I.
      - i. Initially contacted
      - ii. Initial interviewed
      - iii. Consented
      - iv. Baseline data collected
  - e. Reasons for non-participation:
    - i. After initial contact and/or initial interview
    - ii. After consent process
    - iii. After initial data collection or throughout the study
    - iv. Until end of study
  - f. Reasons for participating in and completing study

2) Randomization:

- a. Testing effect of randomization process on distribution of demographic, co-morbidity, and other background characteristics
- f. Testing randomization process on their baseline main outcomes
- g. Examining acceptability of the randomization process and its effect

3) Missing data:

- a. Differences in rates of missing data between medication and placebo groups and per time point
- b. Pattern of missing data

4) Retention rate:

- a. Differences in retention between medication and placebo groups
- b. Factors influencing these differences

5) Subjects' satisfaction with:

- a. Study procedures
- b. Study implementation and staffing
- c. Medication delivery methods
- d. Data collection timepoints and outcomes

6) Medication fidelity with:

- a. Delivery methods
- b. Number of successful and failed deliveries
- c. Assessment methods
- d. Timing and method of feedback

7) Study improvement procedures/maintaining documentation of:

- a. Study/protocol development, revision, and modification
- b. Issues and concerns with implementing recruitment strategies
- c. Issues and concerns with accessing, distributing, and tracking of medication and placebo
- d. Issues and concerns with measurements:
  - i. Number of measurements
  - ii. Time requirements of measurements
  - iii. Redundancy among measurements
  - iv. Positive or negative carryover

Sub-study 1c: FoTv vs placebo for use as an adjunct to COVID-19 vaccination.

The primary objectives of this study are to determine whether FoTv, when taken for four consecutive days starting the day of COVID-19 vaccination, is safe and associated with:

- An enhanced peak COVID-19 antibody response
- A reduced rate of post-peak antibody decline
- Reduction in side effects from COVID-19 vaccination

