### **Sub-study 1c**

Once enrolled, all study participants will receive a package containing the following:

- Four day supply of study medication (capsules containing either FoTv or placebo)
- 
- Written instructions on proper usage of study medication
- Paper study daily diary, to include daily medication diary, symptom scores, and temperature/BP measurement data

During the trial period, participants will be verbally instructed on proper usage of study product and to assess their symptoms. Each participant will receive a paper copy and an emailed study daily diary to record symptoms and symptom scores, medication compliance, and any other medication use.

Participants will be asked to report to the study team any adverse events, either of the study medication or of the vaccination itself, including urgent care, emergency room, or hospitalization.

Subjects will be contacted by phone by the study team 2 weeks after vaccination # 1, 4 weeks after vaccination # 1, 2 weeks after vaccination # 2 (if applicable), 4 weeks after vaccination # 2 (if applicable), 6 months after baseline, and 12 months after baseline to report any symptoms.

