#### **(2) End-of-Treatment:**

For patients who are not hospitalized, the study phlebotomist will collect their specimens at Day 14 for the following laboratory tests:

- Basic Metabolic Panel
- Complete Blood Count with Differential
- Liver Function Testing

- Prothrombin Time and Partial Thromboplastin Time
- Ferritin
- D-Dimer
- Lactate Dehydrogenase
- C-Reactive Protein
- Troponin
- T-cell differentiation panel
- Salivary or nasal swab samples will be collected for SARS CoV-2 viral load assays
- Plasma, serum, and whole blood will be collected and banked for cytokine, immunological, and metabolomic assays

For subjects who require hospitalization by Day 14, results of the following laboratory tests will be obtained from their hospital records (please note that these tests are routinely conducted as part of COVID-19 treatment and results should be available within subjects' medical records):

- Admission Basic Metabolic Panel,
- Complete Blood Count with Differential, and
- Liver Function Testing.

Please note that medical records will also be reviewed for SARS-CoV-2 viral load, any inflammatory biomarkers (CRP, procalcitonin, IL-6, ferritin, D-dimer, lactate dehydrogenase) as well as markers of myocarditis (troponin, CK-MB) and further lymphocyte differentiation (T-Cell differentiation panel).

Sub-study 1c:

Sample collection will occur at the following time points:

- Single dose vaccine (such as J&J): baseline, day 14, day 28, and 6 months post vaccination
- Two-dose vaccine (such as Pfizer or Moderna): baseline, day 14, two weeks after your second dose, and 6 months post vaccination
- Vaccine booster: baseline, day 3, day 14, and 6 months

For all time points:

The following test will be run to establish values of immunogenicity against SARS CoV-2:

- SARS CoV-2 IgG antibody titer
- Cytokines and T-cell assays

For time points Baseline and Day 14:

The following laboratory assays will be conducted to ascertain FoTv safety:

- Basic Metabolic Panel
- Liver Function Tests

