### Test Product Dose and Route of Administration

Participants in sub-studies 1a and 1b: The dosage of FoTv or mQFPD is 8 capsules three times a day for 14 consecutive days. It does not need to be consumed with food. It is best taken at least 30 minutes before OR at least 60 minutes after meals, in the morning, noon and evening. Accidentally missed doses will not need to be taken at a later time, but will be recorded in a daily diary. Should swallowing capsules be an issue, they can be opened and dispensed into water or juice for easy ingestion.

Participants in sub-study 1c: The dosage of FoTv is 8 capsules three times a day for 4 consecutive days ((starting with the day of the first vaccination). It does not need to be consumed with food. It is best taken at least 30 minutes before OR at least 60 minutes after meals, in the morning, noon and evening. Accidentally missed doses will not need to be taken at a later time, but

will be recorded in a daily diary. Should swallowing capsules be an issue, they can be opened and dispensed into water or juice for easy ingestion

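### Sub-study 1c has no on-treatment safety chemistry: the only post-baseline panel comes about 10-11 days after the last capsule, and the booster Day 3 blood is not tested for safety

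*Combined protocol and SAP*

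**What the plan says.** **Exposure.** The sub-study 1c objectives in section 6 ask whether FoTv, "when taken for four consecutive days starting the day of COVID-19 vaccination, is safe and associated with" antibody and side-effect benefits. Section 9 (Sub-study 1c) dispenses a "Four day supply of study medication (capsules containing either FoTv or placebo"). Section 9 (Test Product Dose and Route of Administration) says: "The dosage of FoTv is 8 capsules three times a day for 4 consecutive days ((starting with the day of the first vaccination").

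**Safety chemistry.** In section 9 (Clinical Laboratory Measurements, Sub-study 1c), the Basic Metabolic Panel and Liver Function Tests come under "For time points Baseline and Day 14", followed by "The following laboratory assays will be conducted to ascertain FoTv safety". No other section schedules an earlier safety laboratory test for 1c.

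**Blood draws.** The same section sets draws by regimen. For boosters: "Vaccine booster: baseline, day 3, day 14, and 6 months". For single-dose vaccines: "Single dose vaccine (such as J&J): baseline, day 14, day 28, and 6 months post vaccination". Two-dose recipients also have no draw between baseline and day 14. The assays assigned to every 1c draw, and so the only ones assigned to the booster Day 3 sample, are IgG titer, cytokines and T-cell assays. They are listed as immunogenicity measures.

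**Role of safety.** Sections 6 and 9 both make safety a primary objective of 1c. Statistical Methods and Considerations compares safety data between arms at each time point and tabulates adverse events by occurrence, rate, severity and relationship to treatment.

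**The concern.** Day 14 suits sub-studies 1a and 1b, where dosing lasts 14 days and the draw falls at the end of exposure. In 1c the course lasts four days, so a draw on the same day measures chemistry well after exposure has stopped. Every post-baseline chemistry comparison in 1c would then be an off-treatment comparison.

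This matters because section 7 knows of no human trials of *Fomitopsis officinalis* products, section 14 found no clinical safety data on agarikon, and 1c is the largest FoTv sub-study (266 subjects, against 66 in 1a). Routine panels are there to find changes that cause no symptoms. If such a change rises during dosing and then settles, a Day 14 panel may not show it. Meanwhile a blood sample that probably falls within dosing is drawn from booster recipients and not tested for this purpose.

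**Working it through.** The plan states no interval between last capsule and safety draw, so there is no figure to reproduce. The check is calendar arithmetic followed by a sensitivity range.

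**Step 1. Gap from last capsule to the safety draw.** Inputs: four consecutive dosing days from the day of vaccination (sections 6 and 9); safety draw on Day 14 (section 9). The plan does not say whether vaccination is Day 0 or Day 1, so both are shown.

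- Vaccination = Day 0: dosing on Days 0, 1, 2, 3; gap = 14 − 3 = 11 days.
- Vaccination = Day 1: dosing on Days 1, 2, 3, 4; gap = 14 − 4 = 10 days.

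No visit windows are given for 1c, so these gaps are nominal. For comparison, 14 days of dosing in 1a ends on Day 13 or Day 14, a gap of 1 or 0 days.

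**Step 2. Is the booster Day 3 draw on treatment?** If dosing starts on the booster day, Day 3 is the fourth dosing day (Day 0 count) or the third (Day 1 count), so it is on treatment either way. The condition matters. Section 6 ties dosing to the day of vaccination, while the dosing text in section 9 ties it to the first vaccination and does not say how that applies to a booster.

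**Step 3. How much of a change would remain at Day 14?** The documents give no recovery time for any chemistry effect, so this is an assumption. Take a change at its full size at the last dose that then decays with half-life h. The share remaining after t days is 2^(−t/h).

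| Assumed half-life (days) | t = 10 | t = 11 |
|---|---|---|
| 1 | 0.1% | 0.05% |
| 2 | 3% | 2% |
| 4 | 18% | 15% |
| 7 | 37% | 34% |
| 14 | 61% | 58% |

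To put this on a laboratory scale, assume a baseline of 0.5 × the upper limit of normal (ULN). The highest peak that is back at ULN by Day 14 is 0.5 + 0.5 × 2^(t/h):

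- h = 5 days: 0.5 + 0.5 × 4 = 2.5 × ULN at t = 10, and about 2.8 × ULN at t = 11.
- h = 2 days: 0.5 + 0.5 × 32 = 16.5 × ULN at t = 10, and about 23 × ULN at t = 11.

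The model has no lag: it starts the decay at the last dose. A change that develops after dosing would be more visible at Day 14 than the table suggests, and less visible at Day 3.

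**The case against.** The case for leaving the schedule alone has real substance.

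- **Day 14 is a reasonable common time point.** It is the only draw before 6 months shared by all three vaccine regimens, so it gives one uniform randomised comparison. It can also detect delayed or persistent effects. This stands, and is why Day 14 should be kept.
- **Other safety data exist.** 1c has a daily diary and adverse event reporting, which can catch symptomatic harm during dosing. Sub-study 1a gives the same daily schedule for 14 days, 14/4 = 3.5 times as long, with chemistry at the end of treatment. This lowers the stakes. It does not fill the gap, because diaries do not detect asymptomatic changes, and 1a studies COVID-19 patients with 33 enrolled per arm.
- **Day 3 covers one regimen group only.** Its size is not stated, and section 9 stratifies on age and BMI, not regimen. This stands as a limit on what the change can deliver.

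A reader might also infer four stronger things that the documents do not support.

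- *That a transient effect would certainly be missed.* This depends on an undocumented recovery time. With slow recovery, a third or more of the change could remain.
- *That Day 3 would show the effect at about its full size.* This assumes that the peak comes by the third or fourth dosing day, and nothing in the documents says so.
- *That the plan would treat a null Day 14 comparison as proof of safety.* No section says this. Chemistry is one component beside adverse event tabulation.
- *That the plan breaks its own rule, because section 15 places safety laboratory tests at the end of treatment.* That sentence repeats the distinction between hospitalised and non-hospitalised patients written for 1a and 1b in section 6. It is not clearly a rule for 1c.

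**Conclusion.** The point holds in a limited form. The schedule facts are clear: safety chemistry in 1c is drawn at baseline and then nominally 10-11 days after the last capsule, with no safety panel between. An asymptomatic change that resolves within about 10 days could therefore go undetected. How likely that is cannot be calculated from the documents, and the half-life table is a sensitivity range, not an estimate. Calling the booster Day 3 draw on-treatment rests on dosing starting on the booster day, which section 6 makes likely but the dosing text leaves unclear. For single- and two-dose recipients, the laboratory data can address only persistent or delayed effects. This is an inexpensive improvement that should be made. It does not invalidate the sub-study.

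**What to change.** In section 9, Clinical Laboratory Measurements, Sub-study 1c:

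1. Change the safety-assay time points to baseline, Day 3 (booster recipients, on the existing draw) and Day 14 (all regimens).
2. In the analysis text, report the Day 3 between-arm comparison among booster recipients as on-treatment laboratory safety data, with the number in each arm, and label the Day 14 comparison as post-treatment.
3. State that for single- and two-dose recipients the laboratory data address only persistent or delayed effects.
4. State the day-count convention. Reconcile the section 6 and section 9 descriptions of when dosing starts, so that it is clear how they apply to a booster.

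The cost is two routine panels on blood already being drawn, possibly a slightly larger sample, and a short amendment. The drawback is that on-treatment chemistry will come only from the booster group, whose size is not stated and in which the balance between arms is left to chance. An on-treatment value for the other regimens would need an added draw, which this change does not require.

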### Test Product Dose and Route of Administration

Participants in sub-studies 1a and 1b: The dosage of FoTv or mQFPD is 8 capsules three times a day for 14 consecutive days. It does not need to be consumed with food. It is best taken at least 30 minutes before OR at least 60 minutes after meals, in the morning, noon and evening. Accidentally missed doses will not need to be taken at a later time, but will be recorded in a daily diary. Should swallowing capsules be an issue, they can be opened and dispensed into water or juice for easy ingestion.

Participants in sub-study 1c: The dosage of FoTv is 8 capsules three times a day for 4 consecutive days ((starting with the day of the first vaccination). It does not need to be consumed with food. It is best taken at least 30 minutes before OR at least 60 minutes after meals, in the morning, noon and evening. Accidentally missed doses will not need to be taken at a later time, but

will be recorded in a daily diary. Should swallowing capsules be an issue, they can be opened and dispensed into water or juice for easy ingestion

### **Control Product Dose and Route of Administration**

The placebo control has been developed by the mycelium supplier and contains freeze-dried cooked organic brown rice. It has been encapsulated to a cGMP standard. It has been packaged identically to the test products and appears identical to the verum product (FoTv or mQFPD) by an untrained study participant. Subjects will be instructed to take 8 capsules three times with the same dosing instructions as the study medication for each respective sub-study (1a, 1b, or 1c) as described above.

### **Sample Size Justification:**

We anticipate screening approximately 90 or 300 potential candidates for each sub-study in order to consent and enroll 66 or 266 participants per study 1a/b or 1c respectively.

The primary focus of sub-studies 1b and 1c, as with sub-study 1a, will be on ascertainment of the safety of the natural products under study. The study 1c will also examine efficacy of the mushroom blend.

Therefore, like sub-study 1a, sub-study 1b will also include 27 participants per arm as well as an additional 6 participants per arm to account for an anticipated 20% rate of study dropout. Thus,  $N = (33/\text{arm} \times 2 \text{ arms}) = 66$ .

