## **9. RESEARCH DESIGN AND METHODS**

The following research design applies to each of the following studies:

Sub-study 1a: FoTv vs. placebo for acute COVID-19 patients

Sub-study 1b: QFPD vs. placebo for acute COVID-19 patients

Sub-study 1c: FoTv vs. placebo as an adjunct to COVID-19 vaccination

Sub-studies 1a and 1b of Phase 1 trial will each be 2-arm multicenter double blind randomized placebo controlled clinical trials.

Each of these safety/feasibility sub-studies will be conducted identically with the exception of additional exclusion criteria that will be required for sub-study 1b on account of the presence of herbal components including ephedrine that require these precautions for avoiding herb-drug interactions.

Sub-study 1c will be a single site double blind randomized placebo controlled clinical trial.

This will be a shorter intervention with broader inclusion criteria.

The research design and methods for the larger efficacy trial (Phase 2) will require analysis of these first two feasibility studies, and the final protocol will be submitted as a future amendment.

The primary objective of sub-studies 1a and 1b will be to assess the safety of FoTv or mQFPD, respectively, when used as therapies for acute COVID-19 infection and feasibility of the study protocol.

The primary objectives of sub-study 1c will be to ascertain the safety of FoTv when used as an adjunct to standard COVID vaccination as well as to evaluate its effects on post-vaccine COVID-19 antibody titers and on vaccination-related side effects.

A total of 66 subjects (33 FoTv or mQFPD and 33 placebo) will be enrolled in each of the 1a and 1b sub-studies.

A total of 266 subjects (133 FoTv and 133 placebo) will be enrolled in sub-study 1c.

The study protocol will be implemented and safety, feasibility, clinical, and laboratory data will be collected.

Interested participants will be asked to contact the study team, who will then conduct screening, consenting, and study enrollment. The study will be open to patients who are

- a) Mildly-to-moderately symptomatic and have tested positive for COVID-19 (sub-studies 1a and 1b)
- b) Scheduled for COVID-19 vaccination (sub-study 1c).

See section 11 for recruitment plan.

Once their eligibility has been confirmed, participants will be randomized to one of two groups by the study statistician:

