- Group 1 – either Mycelium of *Fomitopsis officinalis* and *Trametes versicolor* (FoTv) for sub-studies 1a and 1c or modified Qing Fei Pai Du Tang (mQFPD) for sub-study 1b
- Group 2 - Inert placebo (encapsulated brown rice)

We anticipate screening approximately 90 or 75 potential candidates per sub-study in order to consent and enroll 66 or 48 participants to account for up to 20% drop-out rate.

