#### **Sub-study 1c:**

This sub-study will include 266 subjects as well as an additional 53 participants to account for an anticipated 20% rate of study dropout. Number of subjects was adjusted due to recent introduction of the vaccination booster shot and availability of extra funding which allows us to expend study aims to further test of the treatment efficacy.

For other objectives of sub-study 1c, sample size was determined using the RMASS program (<http://tigger.uic.edu/~hedecker/ml.html>)

Based on our sample size estimation, we are confident that the enrollment of 66 (1a/1b) or 266 (1c) participants will provide a sufficient number of subjects to evaluate these outcomes with medium effect size while also ascertaining safety (Tubert-Bitter et al., 2000; Zhang P, 2003).

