### **Statistical Methods And Considerations**

For all sub-studies (1a, 1b, and 1c), data management and statistical analysis will be performed by the Krupp Biostatistical and Data Management Core and will employ the Krupp Data System (KDS). A computer-generated randomization list will be prepared by the study biostatistician and will be used to randomize subjects into one of the two treatment groups with equal probability. For sub-study 1c only, equal number of subjects based on age (18-55 and  $>55$ ) and BMI ( $<30$  and  $\geq 30$ ) will be randomized to the treatment groups. For all sub-studies, randomization tables will be prepared at the beginning of the study and will be maintained by the study biostatistician.

Within each of the sub-studies, the comparability of the two treatment groups in terms of baseline demographic and clinical features will be tested with analyses of variance (ANOVAs) for continuous variables and Chi-square analyses for dichotomous variables. Descriptive statistics and exploratory graphing will be used to assess the distribution, normality, and homogeneity of the data. If needed and applicable, the continuous outcome data will be transformed using an appropriate transformation such as a log transformation. Missing data will be examined to assess randomness and informativeness using methods developed by Diggle (1989). Similarly, we will test whether dropout is random or systematic by comparing the dropouts with the study completers in terms of the baseline data. An absence of significant differences would support the random nature of dropout.

The primary aims of our data analytic strategy will be directed toward assessing the safety of the interventions, antibody titers, vaccine side effects, adherence to treatment, and retention rate. This will help to provide guidance to inform any

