## 10. HUMAN SUBJECTS

Sub-study 1a Fo-Tv vs. placebo:

66 total patients (N=27 in each of two study arms: FoTv and placebo plus an additional 20% per arm to guard against dropout) who have tested positive for COVID-19 and are mildly-to-moderately symptomatic will be included in the study.

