#### **Exclusion Criteria**

1. Any of the following symptoms which, according to the CDC, require hospitalization:
  - a. Trouble breathing
  - b. Persistent pain or pressure in the chest
  - c. New confusion or inability to arouse
  - d. Bluish lips or face
2. Current use of investigational agents to prevent or treat COVID-19
3. Known liver disease (ALT/AST >3x ULN or diagnosis of cirrhosis)
4. Known renal disease (eGFR < 60 ml/min) or acute nephritis.
5. Uncontrolled hypertension (SBP>140 or DBP>90 while on medications)
6. Pregnant or breastfeeding women

Sub-study 1b mQFPD vs. placebo:

66 total patients (N=27 in each of two study arms: mQFPD and placebo plus an additional 20% per arm to guard against dropout) who have tested positive for COVID-19 and are mildly-to-moderately symptomatic will be included in the study.

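### The dropout allowance adds 20% to the target instead of dividing by 0.8, so the enrolment figures do not cover the stated 20% dropout; the effect in 1a and 1b is very small

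*Combined protocol and SAP*

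**What the plan says.** The Sample Size Justification in Section 9 says that, as in 1a, "sub-study 1b will also include 27 participants per arm", with "an additional 6 participants per arm to account for an anticipated 20% rate of study dropout", for a total of 66. Section 10 describes the rule directly for sub-study 1a: 27 in each arm "plus an additional 20% per arm to guard against dropout". It repeats this for sub-study 1b: "mQFPD and placebo plus an additional 20% per arm to guard against dropout". The opening of Section 9 confirms the enrolled number, "A total of 66 subjects (33 FoTv or mQFPD and 33 placebo) will be enrolled", and describes the allowance as made "to account for up to 20% drop-out rate". Allocation is 1:1: the list will "randomize subjects into one of the two treatment groups with equal probability".

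For sub-study 1c, the Sample Size Justification gives 266 subjects "as well as an additional 53 participants to account for an anticipated 20% rate of study dropout". The opening of Section 9, the first paragraph of the Sample Size Justification and the 1c entry in Section 10 all give 266 as the number enrolled or included, with nothing added.

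The plan's statement that the sizes are adequate, at the end of the 1c paragraphs, refers to enrolment of 66 and 266. The Statistical Methods section analyses everyone randomised. It also says that the nonparametric tests use complete data only and that mixed models, which keep participants with missing data, will confirm them.

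**The concern.** An allowance for 20% dropout should leave the target number after one enrolled participant in five is lost. That requires dividing the target by 0.8. Adding 20% of the target gives a smaller number, which falls short of the target when dropout reaches the rate the plan itself anticipates.

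What is at stake is whether the plan's figures deliver what they say. Completion and retention are among the primary interests of 1a and 1b, so the planning statement about dropout should be right. Sub-study 1c is said to be large enough to test efficacy and follows participants for up to 12 months, so the number retained there matters more.

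**Working it through.** **Inputs**

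- Target per arm, 1a and 1b: 27 (Sample Size Justification; Section 10)
- Allowance: 6 per arm, for 20% dropout (Sample Size Justification)
- Enrolled: 33 per arm, 66 per sub-study (opening of Section 9)
- 1c: 266, plus 53 for 20% dropout (Sample Size Justification, sub-study 1c)

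**Step 1. Reproduce the plan's figures.**

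- 1a and 1b: 27 x 1.20 = 32.4, rounded up to 33 per arm and 66 in total. This matches.
- 1c: 0.20 x 266 = 53.2, stated as 53. This matches; 266 + 53 = 319.

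Both allowances are 20% of the target.

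**Step 2. Apply 20% dropout to those enrolled in 1a and 1b.**

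- Retained: 33 x 0.80 = 26.4 per arm, against 27; the gap is 27 - 26.4 = 0.6.
- Dropout rate that the allowance covers: 6 / 33 = 18.2%.
- Enrolment that would cover 20%: 27 / 0.80 = 33.75, rounded up to 34 per arm (68 in total); 34 x 0.80 = 27.2.

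**Step 3. What the 0.6 is worth.** The documents give no derivation of 27 and no numerical effect size or SD, so this step is an illustration under assumed standardised differences d (two-sided 5% level, normal approximation).

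| Quantity | n = 27 per arm | n = 26.4 per arm |
|---|---|---|
| Power, d = 0.5 (assumed) | 45.1% | 44.3% |
| Power, d = 0.8 (assumed) | 83.6% | 82.8% |
| Upper 95% bound on an event rate with no events seen, 1 - 0.05^(1/n) | 10.5% | 10.7% |

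Power changes by less than one percentage point, and the bound by about 0.2 points.

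**Step 4. Sub-study 1c, under each reading of its enrolment.**

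- 319 enrolled: 319 x 0.80 = 255.2 retained, against 266; the gap is 10.8. The allowance covers 53 / 319 = 16.6%. Retaining 266 would take 266 / 0.80 = 332.5, so 333.
- 266 enrolled: 266 x 0.80 = 212.8 retained. There is then no allowance on top of 266, and the question of how to compute it does not arise.

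In the first case, the width of a confidence interval scales with 1/sqrt(n): sqrt(266 / 255.2) = 1.02, or about 2% wider.

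**The case against.** The strongest reply is that the error changes almost nothing in 1a and 1b: 0.6 participant per arm, against a dropout rate described in one place as a ceiling, in sub-studies whose results the plan already says to read with caution. That stands, and it is why the point is minor.

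Three stronger readings are tempting, and the documents do not support them.

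- *The plan depends on 27 completers per arm.* No power, precision or event-rate calculation is tied to 27. The adequacy statement refers to enrolment, and Section 10 says only that 20% is added as a guard.
- *The safety and completion estimates of 1a and 1b will rest on about 26 per arm.* A completion rate has all 33 enrolled in its denominator. Adverse events are tabulated by participants affected, the analysis covers everyone randomised, and dropouts contribute diary data until they leave. Hospitalised participants contribute admission laboratory results. The mixed models keep early leavers. Only complete-data analyses can fall to about 26.
- *A stated precision for 1c is overstated.* No precision calculation for 266 completers appears in the documents, and the shortfall of 11 holds only if 319 are enrolled.

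Nor do retention probabilities make the point larger. With 33 enrolled and 20% dropout, the binomial chance that an arm keeps at least 27 is 0.50, and that both do is 0.50 x 0.50 = 0.25 if the arms are independent. With 34 these are 0.63 and 0.40. Most of that risk is ordinary sampling variation, because the target sits near the mean; dividing by 0.8 does not remove it.

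The reply does not rescue the arithmetic. The plan names 20% as the rate it allows for, its allowance covers 18.2% in 1a and 1b and at most 16.6% in 1c, and no other section repairs this.

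**Conclusion.** The allowance is wrong as written, and the error is minor. In 1a and 1b, 33 per arm leaves about 26 per arm at 20% dropout. This matters only for complete-data analyses, such as the nonparametric tests and the Day 14 laboratory comparisons, and there by a very small amount. In 1c about 255 remain if 319 are enrolled, and about 213 if 266 are. That uncertainty over enrolment is larger than the error in the rule itself.

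The conclusion assumes that the 20% is a share of those enrolled, which is the ordinary meaning of a dropout rate, and that it applies equally in both arms. The figure of 255 also takes 266 as the number before the allowance, as the 1c sample size paragraph reads.

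**What to change.** No extra participants and no change to the analysis are needed.

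1. In the Sample Size Justification and in the Section 10 entries for 1a and 1b, state that 33 per arm gives about 26 completers per arm at 20% dropout, or 27 at about 18%.
2. For 1c, first reconcile the enrolment: 266 in the opening of Section 9, the first paragraph of the Sample Size Justification and Section 10, against 266 plus 53 in the 1c sample size paragraph. Then state completers there as 0.8 x the final enrolment (about 255 or about 213), and base the adequacy statement on that number.

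The cost is a wording change in four places. The downside is that the stated completer numbers become slightly less favourable.
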